Phase I study P188 (NCT03610334, EudraCT 2018-000443-29) was a randomised, double-blind, placebo-controlled, single and multiple ascending dose study to evaluate the safety, tolerability and pharmacokinetics (PK) of IFB-088 when administered to healthy adult subjects. The study consisted of a single ascending dose (SAD) part, and a multiple ascending dose (MAD) part. The study is complete and a total of 72 subjects received IFB-088 or placebo. In the SAD part, 36 subjects received single daily doses of IFB-088 ranging from 2.5 to 60 mg; in the MAD part, 18 subjects received multiple doses of IFB-088 ranging from 15 mg to 50 mg over 14 days. Drug absorption was rapid and maximum concentrations were observed at approximately 1-2 hours (median time at which the C_{max} is observed [T_{max}]) following single and multiple oral dose administration of IFB-088. Dose proportionality was observed for IFB-088 C_{max} and AUC following single daily doses of 10 to 60 mg and multiple daily doses of 15 to 50 mg for 14 days. IFB-088 half-life was 4.6 to 6.2 hours following single doses and 5.7 to 8.4 hours following multiple dosing. The terminal elimination half-lives were similar between Days 1 and 14, suggesting the stationarity (time-independence) of the IFB-088 PK over 14 days. Following repeated bi-daily administration, the drug accumulation ratio ranged between 1.4 and 1.6. Very low concentrations of IFB-088 were evident in urine; the percentage of the administered dose excreted unchanged in urine was < 1%. The primary metabolic pathway proposed in nonclinical studies included the oxidation of IFB-088 to IFB-139 (phase I metabolite) followed by glucuronidation (phase II metabolite), and was confirmed in the P188 study. Based on the population PK model, renal clearance likely marginally contributes to IFB-088 total clearance, while the formation of metabolite IFB-139 by hydroxylation has a major contribution to IFB-088 elimination.

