4.1.4 V2 visit

The V2 visit will occur 4 weeks after V0 (\pm 4 days).

The day before V2 the patient will go on site to be administered the IMP at 20:00. The day of V2 the patient must be present on site around 7:30 as a blood sample for PK will be collected in the morning of V2 before the IMP administration that will take place at 08:00. Patients can, but are not forced to, spend the night at the site between these 2 drug administrations, upon agreement between both parties. Patients who leave far away from the investigational site and cannot be hospitalized during the night before V2 for logistical reasons are allowed to take the evening study treatment at home on the day before V2. In this case, the time of dosing must be set by the study team, depending on the time of planned first PK blood sampling at V2, allowing a 12-hour interval between last drug intake and blood sampling. If the patient cannot take the drug at the exact time requested by the hospital, he must note the actual time of drug intake. Patients who do not spend the night in the hospital must be provided with a sterile container to collect morning urine. It will be given to the patient at V1 for those who will not come to the hospital for drug administration on the day before V2.

The following assessments will be conducted at V2:

- Physical examination and vital signs assessment, according to [Sections 4.2.1.2](#) and [4.2.1.5](#),
- Weight and calculation of BMI,
- 12-lead ECG ([Section 4.2.1.6](#)),
- Blood and urine sample collection for haematology, blood chemistry, urinary analysis according to [Section 4.2.1.8](#),
- Crystalluria analyses according to [Section 4.2.1.9](#),
- PK blood samples collection according to [Section 4.2.2.2](#),

- Query for changes in concomitant medications,
- Recording of AEs (if any),
- Pregnancy test in WOCBP. In addition to tests performed at hospital visits, pregnancy tests will be performed at monthly intervals during treatment and until the end of relevant systemic exposure. If a positive result is detected with urine pregnancy test, a serum pregnancy test will be performed to confirm the results.
- Dispensation of study product to the patient,
- Appointment for the next visit,
- Patients will be given a prescription for blood sampling (creatininemia and eGFR) to be performed at V2 + 1 month in a local laboratory. Results of these analyses will be sent to the site in real time,
- eCRF recording of data collected.

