ABG test measures the pH and the levels of oxygen and carbon dioxide in the blood from an artery. ABG is a sensitive and inexpensive tool for monitoring respiratory function in ALS patients, and turned out to correlate with FVC. ABG does not require patient collaboration and is not influenced by bulbar involvement [41]. Arterial blood samples will be drawn through radial arterial puncture into heparin - lithium Vacutainer polyethylene tubes and immediately analysed using blood gas analyser, routinely calibrated, as appropriate.

Bioelectrical Impedance analysis will be performed using the non-invasive device BIODY XPERT^{ZM}, commercialized by Aminogram. The device is maintained by the patient on his ankle, in seated position, during approximately one minute, during which various parameters are recorded and proceeded by a software. All sites will be trained by Aminogram prior to utilization of the device. Once trained, members of the study team will be allowed to train additional members.

4.2.2.2 *Pharmacokinetic assessment*

Blood sampling for PK assessment will be performed at the V2 visit. The day before V2 the patient will go on site to be administered the IMP at 20:00. If the patient cannot come to the hospital on the day before V2, he will take study treatment at home at the time requested by the site (see [Section 4.1.4](#)). The day of V2 the patient will be administered again the IMP at 08:00. The blood samples for PK will be collected in the morning of V2. Patients can, but are not forced to, spend the night at the site between these 2 drug administrations, upon agreement between both parties.

Venous blood samples (10 mL) for the determination of plasma concentrations of IFB-088 and its hydroxylated metabolite IFB-139 will be drawn by direct venipuncture or via an intravenous catheter into heparin - lithium Vacutainer polyethylene tubes (5x2mL). Samples will be collected at the following time points in the morning: pre-IMP dose, 1, 2, 4 and 6 hours post dose. The actual date and time of each blood sample collection will be recorded.

IFB-088 and IFB-139 concentrations will be measured within one week, using a validated high-performance liquid chromatography with tandem mass spectrometry (HPLC/MS-MS) method. After collection, plasma samples will be stored at -80°C pending analyses. Details of PK blood sample processing, storage and shipping procedures will be provided in the LPM provided by the sponsor.

4.2.2.3 *Biomarkers assessment*

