6.1 INVESTIGATIONAL MEDICINAL PRODUCTS

6.1.1 Dosage and dosage schedule of the investigational medicinal products

The test product, IFB-088, will be administered in 50 mg/day dosage consisting of two uptakes of 25 mg each, as an add-on therapy to riluzole 100 mg. The placebo will be administered in two uptakes, as an add-on therapy to riluzole 100 mg.

Administration of riluzole 100 mg, tablet or suspension, will be at the patient's and/or investigator's choice, as per summary of product characteristics [44]. The daily dose of 100 mg will be taken in two 50 mg doses every 12 hours, at the same time than the IMPs.

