6.1.2 Administration of the investigational medicinal products

Only patients enrolled in the study will receive the study products and only trained and authorised site staff will handle and supply them. Patients will receive the IMPs kit directly from the investigator or the medicine will be sent directly to the patient from the site pharmacy.

The patients will receive the IMP at baseline visit (V0: 2 bottles), V2 (2 bottles) and V3 (2 bottles) visits. They will be instructed to take the IMP orally twice a day (morning and evening uptakes). Intervals for dosing should ideally be about 12 hours (\pm 1 hour). Tablets shall be swallowed with a glass of water 30 minutes before the meal, in fasting condition. For patients who have swallowing difficulties, tablets can be taken in a spoon filled with jellified water. IFB-088 and riluzole will be taken at the same time. Dosage modifications are not permitted. However, in case of unplanned dosage modification by the patient, it shall be documented in the eCRF. Missed doses will not be made up for. In case of vomiting shortly after ingestion of the study product, the patient will leave out the potential missed dose and will take the next dose as normal. Study product doses withheld due to toxicities and AEs will not be made up later. Should the patient or the investigator wish to discontinue treatment for any reason, they may do so at any time. The date of the last uptake will be documented in the eCRF.

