- Worsening (i.e. progression to a higher stage at 6 months compared to the baseline stage defined by ALS-MITOS score): the proportion of progressors will be compared between both treatment groups. The difference in binomial proportions will be estimated along with an exact 95% CI. A sensitivity Bayesian analysis using the historical placebo data from the ProMISe study [26] will be also performed and further detailed in the SAP. Progressors will also be analysed in a logistic regression model adjusting for treatment and additional relevant covariates (specified in the SAP). The treatment effect will be estimated in terms of an odds ratio associated with the 95% CI and p-value and also in terms of a difference in progression rates with its 95% CI using the method proposed by Ge and al. [45].
- Change in King's College score: the endpoint will be analysed with an approach similar to the analysis of ALS-MITOS score.

Analyses of the changes in efficacy endpoints from baseline to month 3 (as inferential analysis) and from month 3 to month 6 (as descriptive analysis) will be also proposed and further detailed in the SAP.

- Respiratory function: changes from baseline to 3 months and from baseline to 6 months will be analysed. Analyses will be further detailed in the SAP.
- Bioelectrical analysis: changes from baseline to 3 months and from baseline to 6 months will be analysed for the planned following parameters: phase angle, Z200/Z5 impedance ratio, skeletal muscle mass, dry mass, and dry mass without fat. Analyses will be further detailed in the SAP.

PK Analysis

Individual plasma concentrations of IFB-088 and IFB-139 (i.e. IFB-088 metabolite) with corresponding nominal sampling times, will be tabulated for each subject and scheduled sampling time, together with descriptive statistics. Mean plasma IFB-088 concentrations profiles by cohort will be presented over time graphically, using blood sampling time (x axis) and concentrations (y axis) on both linear and semi-log scales.

Derived and observed PK parameters will be evaluated by noncompartmental analysis. The following parameters will be listed and summarised by cohort, as appropriate:

- AUC, ng.h/mL,
- C_{max}, ng/mL, with associated T_{max}, h,

- Terminal or apparent terminal $t_{1/2}$, h,
- Apparent systemic clearance (Cl/F, L/h) and apparent volume of distribution (Vd/F, L) at steady state, where F is the overall oral bioavailability of IFB-088.

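### PK sampling ends at 6 h of a 12 h dosing interval, so noncompartmental half-life and Vd/F are unreliable, and AUC and Cl/F need a named interval

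*Protocol*

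**What the plan says.** Protocol 4.2.2.2 draws PK blood at V2 at "pre-IMP dose, 1, 2, 4 and 6 hours post dose". Protocol 6.1.1 gives "50 mg/day dosage consisting of two uptakes of 25 mg each", and 6.1.2 adds: "Intervals for dosing should ideally be about 12 hours". The last sample therefore falls halfway through the interval. The doses around V2 are set for 20:00 the evening before and 08:00 that morning. For patients dosing at home, 4.1.4 asks the site to set the time "allowing a 12-hour interval between last drug intake and blood sampling", and the patient to note the actual time if it differs.

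In Protocol 8.1.5.2, under PK Analysis: "Derived and observed PK parameters will be evaluated by noncompartmental analysis". The list covers AUC, Cmax with Tmax, terminal or apparent terminal half-life, and "Apparent systemic clearance (Cl/F, L/h) and apparent volume of distribution (Vd/F, L) at steady state". The section does not name the AUC interval, the samples that define the terminal slope, or any use of the pre-dose sample as an end-of-interval value. It sets values below the quantification limit to zero. It also plans a population PK model that estimates CL/F, V/F, half-life and AUC and supports dose choice for later studies.

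SAP 2.1.2 lists PK as a secondary objective, but the SAP has no PK analysis section. Protocol 1.1.2.2 reports the phase I results: half-life "5.7 to 8.4 hours following multiple dosing", "the drug accumulation ratio ranged between 1.4 and 1.6", Tmax about 1–2 h, and time-independent PK over 14 days.

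**The concern.** A terminal slope needs samples spread over more than a fraction of a half-life. Here the post-peak samples span 4 h against a half-life of about 6–8 h, and the 2 h sample may still be affected by absorption. Half-life, and any volume derived from it, would then be biased upward and very imprecise in individual patients.

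Clearance raises a different question. At steady state Cl/F equals dose divided by AUC over one dosing interval, and the plan does not say that this is the AUC meant. Other readings would give materially different clearances. All of these are stated secondary endpoints.

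**Working it through.** **Inputs from the protocol.** Sampling at 0, 1, 2, 4 and 6 h; interval τ = 12 h; half-life 5.7–8.4 h; Tmax about 1–2 h; accumulation 1.4–1.6; V2 at 4 weeks. **Assumed.** One compartment; absorption rate ka = 1–2 per h (peak about 1.4–2.2 h, slightly past the phase I range at the top); log-normal residual error, 15% CV for illustration. The documents give no residual error.

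**1. Consistency of the phase I figures.** With k = ln 2 / half-life, accumulation = 1/(1 − e^(−kτ)). A half-life of 5.7 h gives 1.30 and 8.4 h gives 1.59, against 1.4–1.6 stated. The half-life range is a fair input. V2 is at 672 h, and 672/8.4 = 80 half-lives, so steady state is not in doubt for a patient who takes the doses.

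**2. Width of the slope window.** 4/5.7 = 0.70 and 4/8.4 = 0.48 of a half-life.

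**3. Half-life without noise.** At steady state C(t) is proportional to e^(−kt)/(1 − e^(−kτ)) − e^(−ka·t)/(1 − e^(−ka·τ)). For three equally spaced times the log-linear slope depends only on the outer two, so half-life = 4 ln 2 / ln(C2/C6). Example, true half-life 5.7 h and ka = 1: C2 = 0.886 and C6 = 0.626 in relative units, ln(0.886/0.626) = 0.348, and half-life = 2.773/0.348 = 8.0 h.

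**4. Half-life with noise.** At 15% CV the log-scale SD is √ln(1.0225) = 0.149, and the SE of the slope is 0.149 × √2/4 = 0.0527 per h. The probability of no positive slope is Φ(−slope/SE). For true 5.7 h and ka = 2: slope 0.117, ratio 2.22, probability 1.3%. For true 8.4 h and ka = 1: slope 0.0567, ratio 1.08, probability 14%. A profile is more than 50% off when its slope is below k/1.5 or above 2k.

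**5. Clearance under three AUC choices.** AUC(0–6) and AUC(0–12) by linear trapezoid on the sampled points, the latter with the pre-dose value placed at 12 h; AUC(0–∞) as AUC(0–6) + C6/k, using the true k.

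| True half-life, ka | Half-life from 2, 4, 6 h | No positive slope | More than 50% off | dose/AUC(0–6) ÷ true Cl/F | dose/AUC(0–∞) ÷ true Cl/F | Carried AUC(0–12) ÷ true |
|---|---|---|---|---|---|---|
| 5.7 h, 2 | 5.9 h | 1% | 26% | 1.57 | 0.77 | 1.00 |
| 5.7 h, 1 | 8.0 h | 5% | 46% | 1.62 | 0.75 | 1.00 |
| 8.4 h, 2 | 8.8 h | 7% | 37% | 1.69 | 0.62 | 1.00 |
| 8.4 h, 1 | 12.2 h | 14% | 51% | 1.73 | 0.61 | 1.00 |

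The AUC(0–∞) column is close to 1/accumulation (1/1.30 = 0.77; 1/1.59 = 0.63), as it should be. With a log-down trapezoid the carried AUC(0–12) is about 1–2% low instead.

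**6. Does the carried value also rescue half-life?** Only in part. From 4, 6 and 12 h the estimate is nearly unbiased, but at true 8.4 h and 15% CV its 5th–95th percentile range is still about 5.6–17 h.

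**7. Robustness of the carried value.** A pre-dose sample 1 h early or late moves Cl/F by about 4–5%. A true 12 h level 20–30% away from the pre-dose level moves AUC by 3–6%. Replacing a low trough by zero lowers AUC by 10–15%.

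**The case against.** The strongest reply is that the population PK model already delivers clearance, volume, half-life and AUC, and that 8.1.5.2 gives the simulation of new dosing schemes to that model. This stands. A reader might infer that faulty noncompartmental values would feed into later doses; the protocol gives them no such role.

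Second, a reader might infer that clearance cannot be estimated from this design. It can. The words on steady state point to the dosing interval, and the trough sample is already drawn. The 57–73% and 23–39% errors arise only if an analyst takes another AUC. For clearance this is a gap in specification, not in data.

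Third, the size of the half-life problem depends on assumptions. With a peak at 1 h the noise-free bias vanishes (5.7 h reads 5.7 h, 8.4 h reads 8.4 h). The residual CV is assumed, and at 15% about half or more of individual half-lives still fall within 50% of the truth, so calling them mostly noise would go too far. The protocol also hedges by allowing an apparent terminal half-life and summaries as appropriate.

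What remains is that the population analysis is additional. The noncompartmental half-life and Vd/F will still be listed and summarised, and no rule is given for rejecting a slope that spans less than one half-life.

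**Conclusion.** The point holds for noncompartmental half-life and Vd/F: following the stated method gives unreliable values for listed secondary endpoints. Without noise, half-life reads 5.9–8.0 h for a true 5.7 h and 8.8–12.2 h for a true 8.4 h. At 15% CV, 1–14% of profiles give no positive slope and about a quarter to a half are more than 50% off. For AUC and Cl/F the data suffice and only the definition is missing.

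These sizes rest on a one-compartment form, an absorption rate of 1–2 per h, a slope from the 2, 4 and 6 h samples, and an assumed residual error. The primary safety endpoint and the efficacy analyses are untouched, and so is the planned basis for later dose choice. This is a cheap improvement to an exploratory trial's secondary PK reporting.

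**What to change.** In Protocol 8.1.5.2, or in a PK section added to the SAP:

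- Define AUC as AUC(0–12) at steady state, with the pre-dose concentration used as the 12 h value and actual sampling and intake times.
- Define Cl/F as dose / AUC(0–12).
- Do not make the substitution for a patient who missed the preceding evening dose, and do not apply the zero rule for values below the quantification limit to the carried value.
- Report half-life and Vd/F from the planned population PK model only. A slope that includes the 12 h value should be descriptive at most.

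The cost is wording; no new samples are needed. The price is reliance on steady state and on equal evening and morning troughs, and the loss of an individual noncompartmental half-life. Residual error also remains: at 10–20% CV the 5th–95th percentile range of the repaired Cl/F is about 0.94–1.10 to 0.86–1.18 times the true value.

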9. ETHICS

9.1 STATEMENT

This study will be conducted in accordance with all applicable regulatory requirements including the principles of the Declaration of Helsinki and in compliance with this protocol, the requirements of ICH GCP Harmonised Tripartite Guideline Topic E6, Directives 2001/20/EC , 2005/28/ EC of the European Parliament.

The sponsor is obliged to obtain evidence of the investigator's qualification to perform the clinical study. Therefore, the investigator has to provide a dated and signed copy of his professional curriculum vitae (no older than two years and preferably one page-length in English) prior to the start of the clinical study, including information about his experience and training in conducting clinical studies according to the guidelines for GCP.

Written approval must be obtained from the IECs and the CAs in each country before the study can start.

Any modification of the protocol will be made only with the agreement of the sponsor and must be submitted to the IECs and CAs. No changes in the clinical study protocol will be implemented until the amendment and revised ICF (if applicable) have received approval from the IECs and the CAs.

9.2 INDEPENDENT ETHICS COMMITTEE

Prior to the start of the study, the sponsor or investigator will submit the study protocol, patient information, ICF, and other study-related documents, as required by local regulations, to the respective regulatory authorities and the responsible IEC for their written approval. The sponsor or investigator will inform the IEC and regulatory authorities, according to local regulations, about protocol amendments including any new information that require an ethical reconsideration of the study protocol.

When required by the IEC or by local regulation, the sponsor or the investigator will submit to the IEC:

- Information on AEs that are serious and unexpected and associated with the IMP from the investigator's site, as soon as possible,
- Expedited safety reports from the sponsor, as soon as possible,
- Periodic summaries on the status of the study, in accordance with the local requirements and procedures established by the IEC.

9.3 INDEPENDENT DATA MONITORING COMMITTEE

A DSMB without direct involvement in the conduct of the study will be set up to ensure the safety of the participating patients, the relevance of the study and data integrity. DSMB will be composed of at least 3 ALS experts. Each DSMB member will be respectively independent from the sponsor and from the study. DSMB members will monitor safety data and assess patient safety throughout the duration of the study. All safety data occurring during the trial will be forwarded to the DSMB. Roles, responsibilities as well as safety monitoring rules and conventions will be reviewed and

approved by the DSMB at the organisational meeting and included in the DSMB charter. The roles and responsibilities of the DSMB, their operational procedures, and methods of communication with the investigators are objects of the separate DSMB charter.

9.4 INFORMED CONSENT

Prior to a patient's participation in the study, written informed consent must be obtained after the investigator has fully informed the patient or the patient's legally accepted representative of all pertinent aspects of the study. The ICF must be signed and personally dated by the patient or the patient's legally accepted representative and by the investigator according to ICH GCP. The patient or the patient's legally accepted representative must receive a copy of the signed and dated ICF and any other written information provided to the patients.

Any change to the information sheet and the consent form constitutes an amendment and must be submitted for approval to the IEC and the CA.

With the exception of an amendment needed to eliminate hazards to the patients in the study, such amendments may only be put into practice once written approval from the IEC and the CA has been obtained.

The new ICF must be signed and personally dated by the patient or the patient's legally accepted representative and by the investigator and the patient or the patient's legally accepted representative must receive a copy of this signed and dated ICF.

